- Significant increase in antibody titre/area is defined as at least a fourfold increase in HI or a 50% increase in area from non-negative pre-vaccination serum ( $\geq 10$  for HI,  $\geq 4$  for SRH).

**Seroprotection:** Percentages of subjects achieving each of the following thresholds: inverse HI titre  $\geq 40$ , SRH area  $\geq 25 \text{ mm}^2$ : The number and proportion of subjects achieving each threshold at each visit will be tabulated for each vaccine/age group and each vaccine type.

All statistical analyses for HI and SRH will be performed on the logarithmically (base 10) transformed values. Titres below the limit of detection for assays will be set to 1 in 5 for HI and  $4 \text{ mm}^2$  for SRH for the purposes of analysis. Original values will be presented in all listings

The above immunogenicity criteria will be applied to sera collected 21 days after completion of vaccination, i.e., 21 days after the second vaccine dose. For pandemic vaccines, all three criteria should be met.

Should both GSK and Baxter vaccines satisfy all three CPMP criteria, we will compare the immunogenicity of the two vaccines (for each vaccine/age group and each vaccine type) in terms of:

- a. Geometric mean titres 21 days after each vaccination;
- b. Geometric mean ratio increases 21 days after each vaccination;
- c. Seroprotection rates 21 days after each vaccination;
- d. Seroconversion rates 21 days after each vaccination.

Comparisons will be made using parametric or non-parametric tests as appropriate for continuous outcomes, and Pearson's chi-square test or Fisher's exact test where appropriate for categorical outcomes. Further analyses using (generalised) linear models will explore the effect of baseline covariates on the outcomes. For populations (a) and (b), analyses using multiple imputation to allow for missing data will also be undertaken as a sensitivity analysis. No formal adjustment will be made for multiple testing but associated P-values will be interpreted cautiously.

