#### 9.2.6.1 Local and systemic symptoms

The incidences of local and systemic reactions following vaccination will be summarized by vaccine group.

The occurrence of selected indicators of reactogenicity (listed below), which by definition, can only occur up to 6 days post-vaccination, will be recorded on the Local and Systemic Reactions Diary/CRF rather than the Adverse Events CRF.

- Local reactions: Ecchymosis, erythema, induration, swelling and pain at injection site.
- Systemic reactions: Chills, malaise, myalgia, arthralgia, nausea, headache, sweating and fatigue
- Other indicators of reactogenicity: Stayed at home due to reactions, oral temperature, and use of analgesic/antipyretic medication.

If a reaction occurs more than once for a subject, the reaction will be classified according to the highest occurring severity.

All study subjects will be observed for at least 30 minutes after a vaccination for evidence of immediate reactions in general and in particular for symptoms of allergic phenomena (such as rashes, itching, or other allergic manifestations).

Each subject will be instructed to complete a diary card for 7 days following each vaccination, to describe local and systemic reactions and other selected indicators of reactogenicity. If a local and systemic reaction or fever (derived from measured oral temperatures  $\geq 38.0^{\circ}\text{C}$ ) continues beyond the 7-day period after a vaccination, it will also be recorded on the Adverse Events CRF. If the subject recovers on the last day, then this fact will be recorded on the Local and Systemic Reaction CRF.

We will summarise the occurrence of solicited local and systemic symptoms (point estimates and 95%CI) by vaccine type in terms of incidence, intensity, and relation to vaccination. We will use the two-sided Fisher's exact tests to compare groups where appropriate.

Frequencies and percentages (together with 95% CIs) of subjects experiencing each reaction will be presented for each symptom severity. Summary tables showing the occurrence of any local or systemic reaction overall and at each time point will also be presented.

The severity of local reactions, including injection-site ecchymosis, erythema, swelling, and induration, will be categorized as none, 1 to  $\leq 25$  mm, 26 to  $\leq 50$  mm and  $> 50$  mm.

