The severity of pain and systemic reactions will be categorized as none, mild (transient with no limitation in normal daily activity), moderate (some limitation in normal daily activity), and severe (unable to perform normal daily activity).

Distribution of body temperature, staying at home due to vaccine reaction and the use of analgesic/antipyretic medication occurring during 7 days after each vaccination will be tabulated. Fever will be defined as a temperature of  $\geq 38.0^{\circ}\text{C}$ , and severe fever as  $\geq 40.0^{\circ}\text{C}$ . Oral temperature will be categorized as  $< 38^{\circ}\text{C}$ ,  $38^{\circ}\text{C}$  to  $< 39^{\circ}\text{C}$ ,  $39^{\circ}\text{C}$  to  $< 40^{\circ}\text{C}$ , and  $\geq 40^{\circ}\text{C}$ .

All post-vaccination reactions (local and systemic), use of relief medication and absence from work due to any adverse events will be summarized as none *versus* any.

For the local and systemic reaction safety variables, differences among the groups after vaccination will be analyzed by using Pearson's chi-square test or Fisher's exact test where appropriate.

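### For near-ceiling seroprotection and seroconversion rates within age groups, Fisher's exact test is valid but needlessly conservative; Boschloo's exact test would recover about 4 to 18 points of power

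*Protocol*

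**What the plan says.** Section 9.2.5.1 of the protocol compares the two vaccines on seroprotection and seroconversion 21 days after each dose, provided both have met all three licensing criteria. The comparison is made "for each vaccine/age group and each vaccine type". The test for these rates is Pearson's chi-square or Fisher's "exact test where appropriate for categorical outcomes". Section 9.2.5.2 repeats the sentence for the secondary measures. No expected-count threshold is given for moving from one test to the other.

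Section 9.2.1 recruits 60 per group, allows for 17% dropout, and claims 80% power at the 5% level for differences of 10% to 20% in these rates. It states no base rates.

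**The concern.** The head-to-head comparison takes place only after both vaccines have passed. Seroprotection must then exceed 70% in adults up to 60 years and 60% in older adults, in both arms, and it may be much higher. With 50 per arm, the expected number of non-responders falls below 5 once the pooled rate exceeds 90% (50 × 0.10 = 5). Most analysts would then choose Fisher's test.

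Fisher's test conditions on the total number of responders, which the design does not fix. With few non-responders it can take only a few distinct P-values, so its true error falls far below 5%. Boschloo's test also controls the error exactly but fixes only the two group sizes, as the design does. At stake is the chance of seeing a real difference in the proportion of non-responders within an age group, where group sizes are already small.

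**Working it through.** **Inputs.** Evaluable per arm: 60 × 0.83 = 49.8, about 50 (section 9.2.1). Level 5%, taken as two-sided. Allocation 1:1 (section 7.4). The rates are assumptions, because the protocol gives none. The small-count rule is also assumed: the exact test if the smallest expected count is below 5, otherwise Pearson.

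**The plan's own figure.** The 50 evaluable per group reproduces. The 10% to 20% detectable difference cannot be reproduced without base rates. By the normal formula at 50 per arm, an assumed 95% v 75% has 80.9% power, and a 10-point difference reaches at most 63%.

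**Method.** All 51 × 51 tables were enumerated. For rejection region R and true rates a and b, the rejection probability is the sum over R of Bin(x; 50, a) × Bin(y; 50, b). Boschloo's test rejects when Fisher's P is at or below a critical value c, where c is the largest value that keeps the maximum error over all common rates at or below 5%. At 50 v 50, c = 0.0693 and the maximum error is 4.87%. Since c exceeds 0.05, Boschloo's test rejects whenever Fisher's does.

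**True error at 50 v 50.**

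| Common rate | Fisher | Boschloo |
|---|---|---|
| 70% | 3.1% | 4.2% |
| 85% | 2.4% | 3.6% |
| 90% | 1.8% | 3.2% |
| 95% | 0.7% | 2.1% |

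The maximum for Fisher's test at any rate is 3.5%.

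**One case by hand, 100% v 90%.** Only the second arm has non-responders.
- With 0 v 5, Fisher's P = 2 × C(50,5)/C(100,5) = 0.056, which is not significant. It lies below 0.0693, so Boschloo's test rejects.
- With 0 v 6, Fisher's P = 2 × C(50,6)/C(100,6) = 0.027, and both tests reject.
- Power of Fisher's test is P(X ≥ 6) for X ~ Bin(50, 0.10), which is 38.4%.
- Power of Boschloo's test is P(X ≥ 5), which is 56.9%.

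**Power at 50 v 50 under the assumed rule.** Only the exact test used in sparse tables differs between the columns.

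| True rates | Fisher if sparse, else Pearson | Boschloo if sparse, else Pearson |
|---|---|---|
| 100% v 90% | 38% | 57% |
| 98% v 88% | 35% | 46% |
| 98% v 85% | 57% | 67% |
| 95% v 85% | 35% | 39% |
| 95% v 80% | 64% | 66% |
| 95% v 75% | 84.7% | 85.2% |
| 90% v 75% | 53% | 53% |

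The maximum error of the whole two-test procedure is about 5.7% in both columns. It comes from Pearson's test, and the swap leaves it unchanged.

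**Larger comparisons, same rule.** Pooled by vaccine type, with about 150 evaluable per arm, power is 99.8% v 99.9% at 100% v 90% and 95.3% under either choice at 98% v 88%. One corner remains, where one arm is at 100% and the other just below. At 150 per arm c = 0.0616, and 0 v 5 non-responders gives Fisher's P = 2 × C(150,5)/C(300,5) = 0.060, so only Boschloo's test rejects. At 100% v 97% the gain is P(X = 5) for X ~ Bin(150, 0.03), about 17 points. For reactions, with about 180 per arm, c = 0.0576 and the same 0 v 5 table gives 0.061, so neither test rejects. The enumeration found no gain at 180 per arm under this rule.

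**The case against.** The strongest reply is that nothing here is wrong. Both named tests are standard, Fisher's test never exceeds 5%, and the meaning of the qualifier may be settled in a statistical analysis plan that is not shown. The P-values are unadjusted and are to be read cautiously. The supply scenario that section 7.4 calls most likely would make the comparison non-randomised, which matters far more than the choice between two valid tests. All of this stands, and it is why the point is minor.

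A reader might infer three stronger things that the documents do not support:

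- **That the loss applies at 50 per group in general.** It does not. Pearson's test is the named alternative and takes over once tables are no longer sparse. At 90% v 75% the swap changes almost nothing. Where Pearson's test applies it has more power than Boschloo's in the cases computed.
- **That the loss carries over to reactions.** Section 9.2.6.1 summarises "solicited local and systemic symptoms (point estimates and 95%CI) by vaccine type", which means about 180 per arm. Even if Fisher's test were used throughout, the loss there would be at most about 4 points.
- **That section 9.2.6.1 contradicts itself.** One sentence there has "two-sided Fisher's exact tests to compare groups where appropriate"; a later one says "differences among the groups after vaccination will be analyzed by using Pearson's chi-square test or Fisher's exact test where appropriate". Both carry the same qualifier and can be read together. A table such as 20/180 v 34/180 does give P = 0.039 by Pearson and 0.054 by Fisher. But it has 27 expected events per arm ((20 + 34)/2), so it is not sparse and the usual rule selects Pearson's test.

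**Conclusion.** The point holds as a modest, nearly free gain in efficiency. It is confined to age-group comparisons of seroprotection or seroconversion with about 50 evaluable per arm and rates of about 90% or higher. There, Boschloo's test in place of Fisher's adds about 4 points of power (95% v 85%) to 18 points (100% v 90%). At lower rates the gain is about 0 to 2 points.

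The conclusion rests on two assumptions that the protocol does not state: rates near the ceiling, and use of the exact test when an expected count is below 5. Fisher's test remains valid. The swap does not rescue the claim of 80% power for a 10-point difference within an age group: in the 10-point cases at 50 per arm shown above, Boschloo's test reaches at most 57%.

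**What to change.** In sections 9.2.5.1 and 9.2.5.2, state that where an exact two-group test is used for the age-group comparisons of seroprotection and seroconversion, it will be Boschloo's unconditional exact test, two-sided at 5%, in place of Fisher's. Keep Pearson's chi-square for tables that are not sparse. Section 9.2.6.1 need not change on this account.

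The cost is wording, a less familiar test and slightly more computation. It needs no further subjects or samples, and the error of the exact test stays at or below 5%.

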#### **9.2.5.2 Secondary immunogenicity measures**

The secondary immunogenicity measures are:

- a. To identify whether one or two doses of vaccine are required to satisfy the licensing criteria. We will assess whether either GSK or Baxter vaccine is able to meet all three CPMP criteria 21 days after the first vaccine dose. This will be assessed for each vaccine/age group, and each vaccine type;
- b. To examine the kinetics of the antibody responses to vaccination. This will be measured in terms of the ability of GSK or Baxter vaccine to meet any one, or all three, of the CPMP criteria 7 and 14 days after the first and second doses – for each vaccine/age group, and each vaccine type;
- c. To examine persistence of antibody at 6 months. This will be assessed in terms of the proportion of vaccinees who have inverse HI antibody titres of  $\geq 40$ , SRH areas of  $\geq 25\text{mm}^2$ , and inverse MN antibody titres of  $\geq 40$  and  $\geq 80$ . Antibody persistence will be assessed for each vaccine/age group, and each vaccine type;
- d. To evaluate the breadth of the antibody response to the antigenic variant (if appropriate, i.e., an antigenic drift variant emerges prior to the 2010-2011 influenza season). This will be done using the new antigenic variant as test antigen in HI, MN, and possibly by SRH tests by comparing the above primary immunogenicity measures on days 21 and 42 for each vaccine, by age group, and all age groups combined.

As with the primary immunogenicity outcomes comparisons will be made using parametric or non-parametric tests as appropriate for continuous outcomes, and Pearson's chi-square test or Fisher's exact test where appropriate for categorical outcomes. Further analyses using (generalised) linear models will explore the effect of baseline covariates on the outcomes. For populations (a) and (b), analyses using multiple imputation to allow for missing data will also be undertaken as a sensitivity analysis. No formal adjustment will be made for multiple testing but associated P-values will be interpreted cautiously.

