occur. Generally, cases have been limited to laboratory workers or those with occupational swine exposure. However, a pandemic alert was raised in 1976 when swine H1N1 caused an outbreak of respiratory illness with one fatality among 13 soldiers at a military base in Fort Dix, New Jersey, USA. No exposure to pigs was found and sero-epidemiological investigation identified up to 230 further soldiers had been infected suggesting human-to-human transmission. Mass vaccination of the US public was initiated and halted amid reports of adverse vaccine reactions, media scepticism and the lack of pandemic activity.

***Pandemic A/H1N1 emergence in 2009*** In April 2009, near the end of the usual influenza season in the Northern Hemisphere, the first two cases of swine origin H1N1 influenza virus were identified in the United States. The CDC confirmed that these cases were caused by a genetically similar swine virus that had not been previously identified in the United States. Genetic analysis of the strains showed that they were derived from a new reassortment of six gene segments from the known triple reassortant swine virus, and two gene segments (NA and matrix protein) from the Eurasian influenza A (H1N1) swine virus lineage. Effectively all isolates are susceptible to neuraminidase inhibitors, but resistant to M2 inhibitors. The World Health Organization raised its pandemic alert level to Level 6 on June 11 2009, reflecting community level outbreaks of novel H1N1 infection in at least two different WHO regions and the onset of a new pandemic. H1N1 virus has reached over 170 countries and territories worldwide as of August 6 2009, causing at least 177457 cases and 1462 deaths. In the UK, the first pandemic wave is waning, but a substantial increase in cases of novel H1N1 infection is expected following the re-opening of schools in September.

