#### **6.4 Discussion of overall study design**

This study was designed to evaluate immunogenicity of Baxter cell-culture, non-adjuvanted, whole virus H1N1 vaccine, and GSK AS03-adjuvanted, split H1N1 vaccine with respect to Committee of Human Medicinal Products (CHMP) and FDA licensing criteria, and occurrence of local and systemic symptoms and signs following vaccine administration in adult and elderly people who have never previously been vaccinated with pandemic H1N1 influenza vaccine. The exclusion criteria reduce the likelihood of prior pandemic H1N1 infection among vaccinees, but the timing of the study cannot avoid this possibility. Moreover it is possible that a further outbreak of pandemic H1N1 infection may occur during the first 42 days of the study. Nonetheless, this study design was considered best to evaluate the pandemic H1N1 vaccines purchased by the Government. The need for the study was discussed by advisors to the Department of Health. The study proposal was reviewed anonymously as part of the NIHR funding process.

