#### **6.7.5     Removal of subjects from therapy or assessments**

The subject, or where applicable, the subject's legally acceptable representative(s) can withdraw consent for participation in the study at any time without prejudice. The investigator can withdraw a subject if, in his or her clinical judgment, it is in the best interest of the subject or if the subject cannot comply with the protocol.

In addition, a subject may not be eligible for subsequent immunization or may be discontinued from the study following occurrence of:

- Convulsions or any other neurological disturbances after vaccination,
- Hypersensitivity to the investigational vaccine,
- Other suspected side effects that could compromise the subject's wellbeing.

Any subject who, despite the requirement for adequate contraception, becomes pregnant during the trial will not receive further immunization. The site should maintain contact with the pregnant subject, and obtain pregnancy outcome information. It should be noted that pregnant women are at substantially increased risk from pandemic H1N1 influenza. WHO and ACIP recommend the administration of pandemic H1N1 vaccine to pregnant women. It is likely that the Department of Health will also recommend that pregnant women should receive pandemic H1N1 vaccine.

The subject will be followed up after withdrawal, the cause of which will be recorded in detail on the Study Termination CRF, and where appropriate, on the Adverse Events and/or Concomitant Medications CRF. Where the withdrawal of a subject resulted from an adverse event, this will be documented in accordance with the procedures in section 8.6.

Whenever possible, the tests and evaluations listed for the termination visit will be carried out.

Withdrawn subjects will not be replaced.

All subjects who have received investigational vaccines should be included in clinical events assessments, and all who provided pre-immunisation and post-immunisation blood samples at the scheduled times should be included in the immunogenicity assessments.

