**9.2.4 Analysis of immunogenicity criteria**

Blood samples for immunogenicity assays will be collected on Days 0 (prevaccination), 7, 14, 21, 28, 35, 42, and 180.

Antibody response will be evaluated by haemagglutination inhibition (HI), neutralization (MN), and possibly single-radial haemolysis (SRH) in all subjects.

HI and/or MN antibody titres need to be assessed rapidly and so will be analysed in three tranches:

- 1st tranche of sera measuring antibodies before and after 1st injection: Days 0, 7, 14, and 21
- 2nd tranche of sera measuring antibodies before and after 2nd injection: Days 21, 28, 35, and 42.
- 3rd tranche of sera measuring persistence of antibodies: Days 0, 42 and 180.

HI and MN assays will be performed at the Health Protection Agency Centre for Infections, Enteric, Respiratory & Neurological Virus Laboratory, London, UK. SRH tests may be done at the National Institute for Biological Standards and Control. Antibody titrations will be done in duplicate. Pre- and post-vaccination samples from each person will be titrated simultaneously, as specified in the CHMP guidance. The titre assigned will be the geometric mean of two independent determinations.

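### The six-month persistence proportion counts antibody from H1N1 infection after vaccination as persisting vaccine antibody (Protocol 9.2.5.2(c))

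*Protocol*

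**What the plan says.** **The measure.** Protocol section 9.2.5.2(c) sets out "persistence of antibody at 6 months. This will be assessed in terms of the proportion of vaccinees who have inverse HI antibody titres of" 40 or more, together with SRH areas of at least 25 mm² and inverse MN titres of at least 40 and at least 80. "Antibody persistence will be assessed for each vaccine/age group, and each vaccine type". Comparisons of secondary measures use "Pearson's chi-square test or Fisher's exact test where appropriate for categorical outcomes". The definition has no condition on Day 42 status and does not mention infection.

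**The expected exposure.** Section 4.0 says "a substantial increase in cases of novel H1N1 infection is expected following the re-opening of schools in September". Section 6.4 adds: "Moreover it is possible that a further outbreak of pandemic H1N1 infection may occur during the first 42 days of the study". It says nothing about Days 42 to 180 and attaches no consequence for the analysis.

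**Who is analysed.** Section 6.7.5 states that "all who provided pre-immunisation and post-immunisation blood samples at the scheduled times should be included in the immunogenicity assessments". In section 9.2.2, the full analysis set needs one dose and evaluable sera. The per-protocol set removes major protocol violations. Neither names infection.

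**What is measured.** Section 9.2.4 plans a third "tranche of sera measuring persistence of antibodies: Days 0, 42 and 180". The geometric mean ratios listed in section 9.2.5.1 stop at Day 42 over Day 0. GMTs and seroprotection are planned at every visit, Day 180 included.

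**The concern.** Persistence is meant to show how long vaccine-induced antibody lasts. A cross-sectional proportion above a threshold can rise with no contribution from the vaccine if subjects meet the virus in between. Take a subject with an HI titre below 40 at Day 42 who is infected over the winter and has a titre of 40 or more at Day 180. Section 9.2.5.2(c) counts that subject as evidence of lasting vaccine antibody. SRH and both MN thresholds are open to the same misclassification.

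Two conclusions are at stake: the absolute level of persistence for each vaccine, and the between-vaccine comparison. The arm with more subjects below threshold has more subjects whom infection can lift over it.

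**Working it through.** **No figure to reproduce.** The protocol gives no persistence rate, infection rate or power for Day 180. Its only related figure is the 10% to 20% detectable difference in section 9.2.1, stated without a reference rate. The group size used below is 60 × 0.83 = 49.8, so about 50 per vaccine/age group and about 150 per vaccine.

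**Timing.** The start is early September 2009 (section 6.5). Adding 180 days, plus about two weeks of enrolment (section 6.2), puts the last samples at about March 2010, after the rise that section 4.0 expects to begin in September.

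**Model.** Let p be the proportion who would be above threshold at Day 180 without infection. Let r be the share of the remaining subjects lifted over the threshold by infection. Infection of subjects already above the threshold does not change the count.

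- Observed proportion = p + (1 − p)r.
- With equal r in both arms, observed difference = (pA − pB)(1 − r).

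The values of p and r are assumptions:

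| r | Arm A (true 75%) | Arm B (true 50%) | Difference (true 25) |
|---|---|---|---|
| 10% | 77.5% | 55.0% | 22.5 |
| 20% | 80.0% | 60.0% | 20.0 |
| 30% | 82.5% | 65.0% | 17.5 |

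**Effect on power.** This uses a second illustration, 80% v 60%, with a two-sided 5% test. At r = 20% the observed rates are 84% v 68%, so 20 points become 16. Power falls from 59.0% to 46.5% at 50 per group, and from 96.9% to 90.4% at 150 per vaccine.

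**Unequal exposure.** With separate rates, the observed difference is (pA − pB) + (1 − pA)rA − (1 − pB)rB. It widens only if (1 − pA)rA exceeds (1 − pB)rB. At 75% v 50% that is 0.25 rA > 0.50 rB, so rA must be more than twice rB.

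**What a flag can recover.** Take r = 20%, true rates 75% v 50%, and every infection flagged.

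- *Infection only in sub-threshold subjects, flagged subjects excluded:* 0.75/(0.75 + 0.25 × 0.8) = 0.75/0.95 = 78.9%, and 0.50/(0.50 + 0.50 × 0.8) = 0.50/0.90 = 55.6%. The difference is 23.4 points, against 20 unadjusted and 25 true.
- *Same case, flagged subjects counted as not persisting:* 75% v 50%, which is the truth.
- *Infection equally common above the threshold, flagged subjects excluded:* 75% v 50%, again the truth.
- *Same case, flagged subjects counted as not persisting:* 0.75 × 0.8 = 60% v 0.50 × 0.8 = 40%.

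Each handling is exact at one extreme and wrong at the other. Reporting both brackets the answer if flagging is complete.

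**The case against.** **Infection is not invisible.** A reader might infer that infection is looked for only at Visit 1, where influenza-like illness is asked about. The protocol does not support that. The time and events table in section 6.1 repeats the inclusion/exclusion check at Day 21, and criteria 4 to 6 in section 6.7.3 cover confirmed H1N1, antivirals and household cases (although the Visit 4 steps in section 8.1 omit the re-check). The same table marks adverse event monitoring at Day 180. Section 8.6 collects medically attended events and SAEs throughout, and section 6.7.4 records prescription medication during the trial (section 1.2 gives a narrower 21-day window). This objection stands against any claim of no capture. What remains is that no influenza testing is specified, mild or subclinical infection is missed, and nothing ties these records to the persistence analysis.

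**The SAP may deal with it.** Infection rules and sensitivity analyses often sit in a SAP, and section 9.2.2 leaves major violations to be defined before analysis. That is a fair limit on the point. However, the protocol itself fixes the persistence definition, and infection is not a protocol deviation.

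**The direction is not fixed.** A reader might infer that the difference between vaccines must shrink. Section 7.4 calls arrival of only one vaccine the most likely scenario, so the arms may be vaccinated at different calendar times with different exposure. Widening would need more than a twofold imbalance in the example above, but it is possible. The date-of-vaccination covariate in section 9.2.5.3 is offered for the section 9.2.5.1 comparisons and does not identify infected subjects.

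**The size may be small.** Section 4.0 places non-hospitalised cases mainly below age 30, and 240 of the 360 planned subjects are 45 or older. At r = 10% the 2.5-point shift compares with a standard error of √(0.75 × 0.25/50 + 0.50 × 0.50/50) = 9.4 points per age group, or 5.4 points at 150 per vaccine. This stands. In the other direction, section 6.7.1 approaches frontline staff first, which plausibly raises exposure.

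**A restricted main analysis is no cure.** It is tempting to restrict the main analysis to Day 42 responders or to unflagged subjects. Both select on what happened after vaccination, so the compared groups are no longer those allocated. In the worked example, exclusion still gives 78.9% v 55.6%. This objection stands and determines the form of the fix.

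**Conclusion.** The point holds as a modest, inexpensive improvement to one secondary measure. As written, section 9.2.5.2(c) counts infection-induced titres as persisting vaccine antibody during a period when the protocol itself expects infection. Absolute persistence is overstated by (1 − p)r in each arm: 5 and 10 points in the 75% v 50% example at r = 20%. With similar exposure, the difference between vaccines is multiplied by (1 − r). Under sequential allocation, shrinkage is likely but not certain.

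The sizes rest on assumed p and r, and on every counted infection taking the titre over the threshold. The protocol supplies none of these.

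A reader might also infer that the Day 21 and Day 42 results are inflated in the same way, since section 6.4 allows for an early outbreak. The protocol gives nothing from which to size that, and it is not part of this conclusion.

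**What to change.** Keep the all-vaccinee Day 180 proportion as the main persistence measure and add to section 9.2.5.2(c):

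1. The Day 180/Day 42 geometric mean ratio by vaccine and age group, from the paired third-tranche titres.
2. A prespecified sensitivity analysis for HI, MN and SRH that flags subjects with any of: recorded laboratory-confirmed H1N1; antiviral treatment for influenza-like illness; or a rise from Day 42 to Day 180 of at least fourfold in HI or MN, or at least 50% in SRH area. The HI and SRH limits match the plan's own definition of a significant increase. Report persistence twice: with flagged subjects excluded, and with flagged subjects counted as not persisting.
3. A statement that the correction is partial. A subject at HI 160 on Day 42 who wanes to 20, is infected and returns to 160 shows no net rise and is not flagged on titre. Nor is a subject who goes from 20 to 40.

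Optionally, ask about influenza-like illness, H1N1 testing and antivirals at the existing visits after Day 0. A later SAP could not recover that information.

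**Cost:** a little extra analysis and a slightly smaller denominator where flagged subjects are excluded. No additional sera are needed. The optional questions add a short CRF item.
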